1.3. GLOSSARY OF ABBREVIATIONS

Abbreviation	Definition			
AE	Adverse event			
AESI	Adverse events of special interest			
ALP	Alkaline phosphatase			
ALT	Alanine aminotransferase			
аРТТ	Activated partial thromboplastin time			
AST	Aspartate aminotransferase			
ATC	Anatomical Therapeutic Classification			
BPM	Beats per minute			
CBC	Complete blood count			
CI	Confidence interval			
CMP	Comprehensive metabolic panel			
CNS	Central nervous system			
CR	Complete response			
CRF	case report form(s) (paper or electronic as appropriate for this study)			
CRS	Cytokine release syndrome			
CT	Computed tomography			
CTCAE	Common Terminology Criteria for Adverse Events			
DCR	Disease control rate			
DLT	Dose limiting toxicity			
DOR	Duration of response			
DRR	Durable response rate			
DSMC	Data safety monitoring committee			
ECOG	Eastern Cooperative Oncology Group			
eCRF	Electronic case report form			
EOT	End of treatment			
FDA	Food and Drug Administration			
ICANS	Immune effector cell-associated neurotoxicity syndrome			
ICE	Intercurrent events			
ICF	informed consent form			
ICH	International Council for Harmonization			
IgG	Immunoglobulin G			
INR	International normalized ratio			
irAE	Immune-related adverse event			
iRECIST	Immune response evaluation criteria in solid tumors			
ISR	Injection site reaction			
ITT	Intent-to-treat			
LDH	Lactose dehydrogenase			
MedDRA	Medical Dictionary for Regulatory Activities			
MRI	Magnetic resonance imaging			

Abbreviation	Definition		
NCI	National Cancer Institute		
NE	Not evaluable		
ORR	Overall response rate		
OS	Overall survival		
PD	Progressive disease		
PD-1	Program death receptor - 1		
PD-L1	Programmed death ligand 1		
PFS	Progression-free survival		
PR	Partial response		
PT	Prothrombin time		
PT	Preferred term		
PTT	Partial thromboplastin time		
PV	Poliovirus		
QW	Once weekly		
Q3W	Every three weeks		
Q4W	Every four weeks		
RECIST	Response evaluation criteria in solid tumors		
SAE	serious adverse event		
SAP	Statistical analysis plan		
SD	Stable disease		
SOC	System Organ Class		
T3	triiodothyronine		
T4	thyroxine		
TCID	Tissue culture infectious dose		
TEAE	Treatment-emergent adverse event		
TESAE	Treatment-emergent serious adverse event		
TSH	Thyroid stimulating hormone		
ULN	Upper limit of normal		
WBC	White blood cell		
WHO-DD	World Health Organization Drug Dictionary		

2. OBJECTIVES

Objective	Endpoint
Primary	
To evaluate the antitumor activity of lerapolturev with and without anti-PD-1, in participants who have failed anti-PD-1/L1based therapy	Overall Response Rate (ORR): the proportion of participants achieving confirmed complete (CR) or partial response (PR), per RECIST 1.1 criteria.
To evaluate the safety/tolerability of lerapolturev with and without anti-PD-1, in participants who have failed anti-PD-1/L1based therapy	 The frequency and severity of treatment-emergent adverse events (TEAEs) via National Cancer Institute (NCI) Common Terminology Criteria for Adverse Events (CTCAE, v5.0) Changes in laboratory (hematology, chemistry) parameters Changes in vital sign parameters The frequency and severity of lerapolturev AESI The frequency and severity of anti-PD-1 immune-related AE (irAE) Study treatment discontinuation due to AEs
Secondary	•
To evaluate survival and disease control outcomes of lerapolturev with and without anti-PD1, in participants who have failed anti-PD-1/L1based therapy	 Overall survival (OS): time from treatment group assignment until death from any cause Duration of Response (DOR): time from confirmed objective response (CR or PR per RECIST 1.1) until unequivocal disease progression or death, whichever occurs first Disease control rate (DCR): the proportion of participants achieving confirmed CR, confirmed PR, or SD per RECIST 1.1, as best response Disease control rate-6months (DCR-6mo): the proportion of participants achieving confirmed CR (any duration), confirmed PR (any duration), or SD (≥ 6 months) per RECIST 1.1 as best response Durable Response Rate (DRR): the proportion of participants with confirmed CR or PR (per RECIST 1.1) lasting at least 6 months Progression-free survival (PFS): time (number of months) from treatment group assignment until date of documented radiologic disease progression per RECIST 1.1 or death due to any cause, whichever comes first

3. GENERAL STATISTICAL CONSIDERATIONS

3.1. SAMPLE SIZE AND POWER

The determination of sample size in this two-arm, randomized open-label Phase 2 trial was based on feasibility and logistical considerations. As discussed in Protocol Section 1.1, the Sponsor estimates that the true activity of anti-PD-1 re-challenge in the anti-PD-1 refractory population eligible for this study is less than 10%. Therefore, lerapolturev administered in combination with anti-PD-1 therapy using the QW injection schedule, will be considered to have anti-tumor activity in the anti-PD-1 refractory melanoma population if the lower bound of the 95% CI is above 10%. We estimate the sample size for participants receiving lerapolturev (QW schedule) ± anti-PD-1 therapy to be approximately 30 participants (n=15 per arm). Therefore, 5 of 15 participants (ie, 33%) in Arm 2 treated with the lerapolturev/anti-PD-1 combination (QW schedule) must have an objective response for the 95% CI to be greater than 10% (95% CI: 11.8% to 61.6%).

3.2. HANDLING OF DATA

3.2.1. Strata and Covariates

Participants receiving lerapolturev injections using the Q3/4W schedule \pm anti-PD-1 therapy will be stratified based on time since prior anti PD1/L1 exposure (\leq 6 weeks versus > 6 weeks) and baseline LDH (normal versus > upper limit of normal [ULN]).

Participants receiving lerapolturev injections using the QW schedule \pm anti-PD-1 therapy will be stratified based on type of anti-PD-1/L1 resistance (primary versus secondary as defined in Kluger et al) and baseline LDH (normal versus > ULN).

For statistical summary presentation, summaries, for the following subgroups will be presented:

- lerapolturev monotherapy on the QW schedule
- lerapolturev monotherapy on the Q3/4W schedule
- lerapolturev + anti-PD-1 on the QW schedule
- lerapolturev + anti-PD-1 on the O3/4W schedule
- all crossover to lerapolturev + anti-PD-1 participants
- lerapolturev + anti-PD-1 plus crossover participants (all lerapolturev + anti-PD-1)
- overall treated participants

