Anyone transitioned from warfarin to an oral anticoagulant prior to the first dose of lerapolturev should have an INR < 1.5x upper limit of normal in order to participate. Antiplatelet agents (eg, aspirin, clopidogrel, etc.) are not considered anticoagulants for the purposes of this study (ie, are allowed) 21. A pregnant or nursing female, or women of child-bearing potential and men who are sexually active and not willing/able to use medically acceptable forms of contraception starting from signed ICF through 150 days after last anti-PD-1 dose 22. History of human serum albumin allergy 23. History of neurological complications due to polio virus infection 24. History of agammaglobulinemia 25. Concurrent participation in a separate interventional clinical trial during this study 26. Any underlying medical condition for which, in the opinion of the investigator, participation would not be in the best interest of the participant (eg, compromises the participant's wellbeing) or that could prevent, limit, or confound protocolspecified assessments Concomitant Pembrolizumab or nivolumab (Arm 2 only) **Treatment** Lerapolturev (formerly PVSRIPO): Oncolytic Polio/Rhinovirus Investigational Recombinant **Drugs** Up to approximately 30 sites Planned Study Sites Criteria for Efficacy: Changes in skin lesion and/or radiographic tumor measurements and survival will be assessed per RECIST 1.1 at Assessments regular intervals to evaluate efficacy: participants achieving objective response (along with associated durations) or disease control by Week 26 or upon anti-PD-1 re-challenge (Arm 1 and safety run-in participants that crossover to Arm 2, analyzed from time of crossover but separately from Arm 2) through study completion. Assessment of anti-tumor response by iRECIST will be exploratory. **Safety:** Laboratory and spontaneously reported AEs, to evaluate safety and tolerability to determine incidence and severity of treatment-emergent AEs for duration of the study

Confidential Page 17 of 109

	Biomarkers: Biological samples will be collected as indicated in the schedule of assessments (SOA) to evaluate immune, genetic, or cytologic factors impacting lerapolturev mechanism of action (MOA), anti-tumor response, and/or to evaluate immune-related AEs

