Any participant from the safety run-in cohort is allowed to crossover to combination therapy after completion of the safety run-in, as described in Section 3.1.1. However, these participants will be analyzed separately, and will not contribute to the population enrolled to establish the anti-tumor activity of the lerapolturev/anti-PD-1 regimen.

Lerapolturev Dose, **QW** Schedule: Given the slight increase in the lerapolturev dose and increased frequency of dosing during the first 2 months on treatment, the DSMC will review all safety data once 12 participants have started the weekly x 7 "induction" series of injections (ie, n=6 monotherapy and n=6 combination with anti-PD-1) and have cleared the DLT evaluation period (ie, 21 days after Cycle 1, Day 1). Applying the same rules as used for the original safety run-in, should an excessive DLT rate (ie, >33%) be detected, the lerapolturev dose (ie, the maximum number of lesions and/or maximum TCID₅₀ dose) and/or the number of weekly injections may be decreased in one or both treatment arms, based on DSMC recommendations. See Section 3.1.4 for the DLT definitions.

Confidential Page 53 of 109

NOTE: For Arm 2 (lerapolturev/anti-PD-1 combination), AEs should only be considered a DLT if judged by the investigator to be related to lerapolturev and of increased severity/frequency compared to what is expected with administration of single-agent anti-PD-1 therapy in this population, or if it is refractory to common management practices due to lerapolturev.

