8.5.4 Exploratory Analyses

Exploratory objectives evaluating subgroup analyses, such as outcomes for participants based on BRAF status, primary versus secondary resistance, time since prior anti-PD-1 administration, responses following Arm 1 to Arm 2 crossover (ie, anti-PD-1 re-challenge),

Confidential Page 82 of 109

baseline LDH levels or others (as described in Section 2.1) will be summarized by endpoints, including DOR, DRR, DCR, PFS and OS. DRR will be presented as the number (%) of participants with CR or PR lasting ≥6 months, along with 95% CI. DCR will be shown as the number (%) of participants with SD, PR, or CR together with the 95% CI. DOR, PFS and OS will be described using the Kaplan-Meier method. For the analysis of response following crossover from Arm 1 to Arm 2, the baseline for anti-tumor response in this subgroup will based on the size of the tumor at the time of crossover and will be summarized separately. Anti-tumor response (ie, ORR, DOR, and DRR) based on iRECIST will also be summarized with descriptive statistics, as appropriate.

In addition, a per-protocol population (no major protocol deviations, etc.) and predictors of lerapolturev response and/or changes in markers of immune function will be summarized by summary statistics, as appropriate. Additional details regarding these and other analyses will be described in the SAP.

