3.2.6. Definitions and Terminology

Age

Age is age at informed consent and is as captured on the eCRF.

CONFIDENTIAL Page 19 19 November 2024

Baseline Value

For purposes of analysis, the baseline value is defined as the last non-missing value obtained prior to initiation of study drug.

Cycle 1, Day 1 (Baseline)

Cycle 1, Day 1 is the earliest day that study drug is initiated.

Study Day

Study Day is defined relative to Baseline (Cycle 1, Day 1). Thus, the study day of an event is calculated as:

Study Day = event date – date of Cycle 1, Day 1 (+ 1, if event date \geq date of Cycle 1, Day 1).

Study Visit

Study Visit is the nominal visit as recorded on the eCRF.

Change from Baseline

Change from baseline for a given endpoint is defined as the Study Day X value minus the Baseline Value.

Days on Study

Days on study is the number of days from Cycle 1, Day 1 to the date of study completion as recorded on the End of Study eCRF page.

Adverse Event (AE)

An AE is any untoward medical occurrence in a patient or clinical study participant, temporally associated with the use of study drug(s), whether or not considered related to the study drug(s). An AE can therefore be any unfavorable and unintended sign (including an abnormal laboratory finding), symptom, or disease (new or exacerbated) temporally associated with the use of study drug(s).

Treatment-emergent Adverse Event (TEAE)

A TEAE is an AE that occurred during the study on or after the initiation of study drug through 30 days after last dose of study drugs. Additionally, it is assumed that an AE which was reported to have started on Cycle 1, Day 1 without an associated onset time occurred on or after initiation of study drug. Treatment-emergent serious adverse events (TESAEs) are collected through 90 days post last dose of study drug.

Adverse Event of Special Interest (AESI)

Any AE (serious or non-serious) of scientific and medical concern for which ongoing monitoring and communication by the investigator to the Sponsor or designee may be appropriate. Such events may require further investigation to characterize and understand them.

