4.2. EFFICACY

Participants receiving at least one lerapolturev injection and at least 1 post-baseline assessment. If a participant crosses over from monotherapy to combination therapy, then the treatment analyzed will be based on the treatment for that participant at the time of the assessment for the efficacy set.

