7. CHANGES IN THE PLANNED ANALYSES

The following exploratory analysis listed in protocol will no longer be conducted.

- ORR/DOR, DRR, DCR, and DCR-6mo based on iRECIST criteria
- ORR, DOR, DRR, DCR, and DCR-6mo in the following subgroups:
 - o Acquired versus primary PD-1/L1 resistance, as defined by Kluger, et al
 - o BRAF wild type and mutant
 - o LDH levels at baseline
 - \circ Time since last dose of anti-PD-1/L1 therapy prior to randomization (\le or > 6 weeks)
 - o Crossover to combination arm from lerapolturev monotherapy
- OS and PFS in the following subgroups:
 - o According to treatment arm and AJCC stage at baseline
 - o Acquired versus primary PD-1/L1 resistance, as defined by Kluger, et al
 - o BRAF wild type and mutant
 - o LDH levels at baseline
 - \circ Time since last dose of anti-PD-1/L1 therapy prior to randomization (< or > 6 weeks)
 - o Crossover to combination arm from lerapolturev monotherapy

8. REVISION HISTORY

Date	Revision	Rationale
10OCT2024	 Update PFS definition to be censored at last imaging instead of death. Update tables that were using the ITT Population to Safety Population. 	 Last imaging is more appropriate here since we are looking at Progression-free Survival. ITT does not include Safety Run-ins since those subjects are not randomized.

9. REFERENCES

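### The SAP gives tumour response no crossover baseline and adds a pooled Arm 2 plus crossover efficacy column, although the protocol sets the baseline at crossover and keeps crossovers apart from Arm 2

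*SAP*

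**What the plan says.** **Protocol.** The synopsis (Criteria for Assessments) has Arm 1 and run-in participants who cross over "analyzed from time of crossover but separately from Arm 2". Section 8.5.4 adds that "the baseline for anti-tumor response in this subgroup will based on the size of the tumor at the time of crossover" and that the results are summarised separately. For run-in participants only, section 3.1.3 says that "these participants will be analyzed separately, and will not contribute to the population enrolled to establish the anti-tumor activity of the lerapolturev/anti-PD-1 regimen". The schedules of assessments in both documents require re-baseline imaging within 28 days before the first combination dose.

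**SAP.** Section 3.2.6 gives one baseline: "the baseline value is defined as the last non-missing value obtained prior to initiation of study drug". Partial response (PR) is a fall of at least 30% from the baseline sum of diameters with no new lesions. Progression (PD) is a rise of at least 20%, and at least 5 mm, from the smallest sum on study, or a new lesion. When a participant crosses over, section 4.2 says "then the treatment analyzed will be based on the treatment for that participant at the time of the assessment for the efficacy set". Sections 3.2.1 and 5 list seven presentation groups for all summary tables and figures. They include Arm 2 by schedule, "all crossover to lerapolturev + anti-PD-1 participants", and the pooled group "lerapolturev + anti-PD-1 plus crossover participants (all lerapolturev + anti-PD-1". Section 7 lists analyses no longer conducted; under response it names "Crossover to combination arm from lerapolturev monotherapy".

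**The concern.** Response needs a reference measurement. The SAP gives overall survival and progression-free survival a time-of-crossover origin in 3.2.6, but gives response no counterpart, and none of its derivations uses the re-baseline scan. Someone programming from the SAP alone would measure post-crossover scans against the pre-study sum and attribute the result to the combination. Someone programming from protocol 8.5.4 would use the sum at crossover. The same data would then yield two crossover response rates.

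The pooled column is the second problem. It puts those responses beside Arm 2 responses in one rate for the combination, which the protocol rules out for response. SAP 7 declares neither the pooling nor any change of baseline. What is at stake is the credibility of any response rate reported for crossover participants, or for everyone who received the combination.

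**Working it through.** **1. The plan's own figure.** The rule (SAP 3.1, protocol 8.3) is a lower 95% bound above 10% in Arm 2 on the weekly schedule, with n = 15. Clopper-Pearson limits: 5/15 gives 11.8% to 61.6%, as stated; 4/15 gives 7.8% to 55.1%. Five is therefore the minimum. Nothing below changes this.

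**2. Fall needed for PR under the literal baseline.** Let g be the proportional change in the sum from pre-study to crossover. PR requires a sum of at most 0.70 × pre-study, so the change required from crossover is 0.70/(1 + g) − 1.

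| Change at crossover (g) | Change from crossover needed for PR, SAP read literally | Needed under protocol 8.5.4 |
|---|---|---|
| +20% | −41.7% | −30% |
| +30% | 0.70/1.30 − 1 = −46.2% | −30% |
| +50% | −53.3% | −30% |
| −20% | −12.5% | −30% |
| −30% | 0% | −30% |
| −40% | 0.70/0.60 − 1 = +16.7% (growth allowed) | −30% |

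**3. Worked cases** (illustrative sums, pre-study = 100).
- Crosses over on progression at 130, later 85: −15.0% from pre-study, not PR; 85/130 − 1 = −34.6% from crossover, PR.
- Crosses over on progression at 130, later 125: +25.0% from the study nadir of 100, PD; 125/130 − 1 = −3.8% from crossover, stable disease.
- Crosses over in PR at 60 and stays there: −40.0% from pre-study, so two post-crossover scans give a confirmed PR on the combination; 0% from crossover, stable disease.
- Progressed through a new lesion: the lesion still counts as new relative to the pre-study scan, so PR is not available however far it shrinks.

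Progression and a PR lasting at least 6 months are both crossover criteria in protocol 3.1.1, so both directions of error are foreseeable.

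**4. Weight of crossovers in the pooled column.** Protocol Table 3, at 10 December 2021, has 13 participants in its pooled combination group: 6 from Arm 2 and 7 crossovers, 7/13 = 54%. The final number is not given. Assume 15 in Arm 2 on the weekly schedule, the 6 earlier Arm 2 participants, the 7 earlier crossovers and no further crossovers from the old schedule:
- no weekly-schedule Arm 1 participant crosses over: 15 + 6 + 7 = 28, crossovers 7/28 = 25%;
- all 15 cross over: 28 + 15 = 43, crossovers 22/43 = 51%.

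**5. What one re-scored participant does to that column.** At n = 28, 6 responders give a lower bound of 8.3% and 7 give 10.7%. At n = 43, 8 give 8.4% and 9 give 10.04%. One PR carried in from monotherapy can move the pooled lower bound across the 10% line. The plan does not apply its rule to this column, but a reader could.

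**The case against.** The strongest reply is that the primary decision is untouched, and on the documents that stands. A reader might infer that pooling puts crossover participants into the randomised arm that carries the 10% rule. The documents do not support this. SAP 3.1 ties the rule to Arm 2 on the weekly schedule, SAP 3.2.1 and 5 give that group its own column, crossovers have a separate column, and SAP 5.6.1 ends primary response for Arm 1 and the run-in at crossover. The protection is implied, however: SAP 4.2 assigns treatment at the time of assessment, and no sentence bars post-crossover assessments from the Arm 2 columns.

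Second, pre-study scoring is an inference from a general definition plus silence. The protocol lets the SAP prevail only where the two disagree, so silence could leave 8.5.4 in force, and sites could use the re-baseline scan for their timepoint responses. That is fair. The defect is an omission that permits a wrong derivation, not a rule that orders one.

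Third, if SAP 7 governs, no crossover response is reported and the scoring problem disappears from the crossover column. But SAP 3.2.1 and 5 require crossover and pooled columns in the response table, and both instructions cannot be followed.

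Three further limits stand. Protocol 3.1.3 covers run-in participants only, so it cannot be cited for Arm 1 crossovers. A carried-over PR needs confirmation, so it is not credited on one scan. Pooling for safety matches the protocol's own Table 3, and the protocol asks for a crossover baseline for anti-tumour response only, so laboratory and vital-sign baselines are not at issue.

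**Conclusion.** The point holds for efficacy outputs. The SAP lacks a crossover baseline for response, adds a pooled efficacy column that the protocol's separation does not allow, and contradicts itself on whether crossover response is reported.

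Read literally, the baseline error runs both ways: a 46% fall is needed after 30% growth, and none is needed after a 30% reduction. These figures follow from the SAP's definitions; the example sums are assumed. Crossovers were 54% of the protocol's pooled group at the December 2021 cutoff and would be 25% to 51% of the final pooled column under the stated assumptions.

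The Arm 2 weekly-schedule result and its 5-of-15 rule are not shown to be affected. Crossover response is exploratory and the analyses are descriptive, so this should be fixed before tables are produced, but it does not threaten the primary conclusion.

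**What to change.** 1. SAP 3.2.6: for crossover efficacy columns, define the tumour baseline as the last assessment before crossover Cycle 1 Day 1, and count nadir and new lesions from that point.
2. SAP 3.2.1 and 5: remove the pooled Arm 2 plus crossover column from efficacy outputs. It may stay for safety.
3. SAP 4.2: state that post-crossover assessments do not enter the Arm 2 columns.
4. SAP 7: reconcile with 3.2.1 and 5, so that crossover response is either reported separately from the crossover baseline or not reported.

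The cost is SAP wording and one derived baseline. The re-baseline scan is already mandated, so no new data are needed.

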3.2.2. Multiple Testing and Comparisons

All analyses will be conducted without adjustments for multiple comparisons.

